5.3 Covariates and Subgroups

There will be no covariate or subgroup analysis in the phase 1 component of this protocol.

For the phase 2 component of the study, the following subgroups may be used to further summarize and evaluate the efficacy endpoints, if sufficient data are available:

- Risk of recurrence (High risk vs intermediate risk)
- Carcinoma in situ (yes vs no)
- Patient immune response
- TNM stage, grade, and severity
- BCG naïve or BCG recurrent; number of prior BCG treatments
- Screening TURBT characteristics (Re-resection TURBT at screening, muscle in specimen)
- Number of prior TURBTs
- Number and size of tumors
- TIL status
- Demographics
- Academic vs. Community practices
- Use of Blue Light cystoscopy
- Use of peri-operative chemotherapy

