### 6.3 Long-term Follow-up Visits

All patients will be followed for the procedures listed below every 3 months from the date of the previous visit for 2 years then every 6 months from the date of the previous visit for a year or until study termination, whichever occurs first:

- Survival
- New anticancer treatments initiated after disease recurrence
- TURBT or fulguration procedures
- Cystectomy

In addition patients who have completed all study treatments or have discontinued study product dosing due to reason other than disease recurrence/progression will have the following procedures performed at each long-term follow-up visit:

- Cystoscopy/Cytology; biopsy if area suspicious for disease recurrence is identified at discretion of investigator (*Note: patients who have a biopsy performed will provide at least 4, non-stained, 10 micron sections for TCR sequencing and analysis of infiltrating T-cells.*) *If slides are not available, FFPE tissue (≥50 microns) is also acceptable.*

If a patient has recurrent/progressive disease and discontinues study treatment, the above disease assessment procedures will be discontinued, and subsequent long-term follow-up visits may be conducted via phone visit.

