The frequency of IFN $\gamma$  producing CD8+ cells is thought to mirror the frequency of cytotoxic CD8+ cells. However, cytotoxicity is primarily mediated by perforin and granzymes following granule exocytosis. In some instances IFN $\gamma$  secretion and granule exocytosis are uncoupled. Therefore, the direct measurement of grzB secretion by ICS may provide a more direct readout for antigen-specific granule exocytosis and cytotoxicity. For clinical efficiency it may be important to detect both IFN $\gamma$  secretion and grzB exocytosis. Antigen specificity of the ICS response will be evaluable by comparing responses generated using the various stimulator cell populations and specific shared bladder cancer antigens as indicated. This will also enable separation of the ‘allo-antigen’ specific response with the potential parent cell line tumor-antigen-specific response. Positive responses will be defined as a greater than two-fold increase in the number of IFN $\gamma$  positive CD8+ T cells compared to baseline.

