#### **10.2.5 Analysis of Infiltrating T Cells (Post-Treatment Tumor Biopsy)**

If a biopsy is performed at any time post-treatment, the tissue will also be examined for presence of infiltrating T-cells (TILs). Two-color fluorescence immunohistochemistry (IHC) and multicolor fluorescence-activated cell sorting analysis will be used for quantification of CD8+ T cells and measurement of their activation status (CD69-expression) and cytotoxic activity (CD107a-expression) *in situ*. These data will be correlated with clinical response.

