#### **10.2.6 Antigen Screening of Resected Tumor Tissue**

A sample containing at least 4, non-stained, 10 micron sections will be collected for the purpose of screening the tissue for representative antigen expression (LAGE-1, NY-ESO-1, MAGE-[A1-10], CT7, CT10, GAGE, etc.), expression of MHC class I, and expression of immunosuppressive molecules, including, for example, CTLA-4, PD-L1 and PD-1, by mRNA expression and/or IHC analysis. If slides are not available, FFPE tissue ( $\geq 50$  microns) is also acceptable. These data will be retrospectively correlated with immune response to determine if a particular antigen expression profile may predict response to treatment.

The tumor arrays will be processed by IHC and PCR according to standard methods. Bound antibodies will be visualized by using the avidin-biotin complex method according to the recommendations of the supplier (Vectastatin Elite ABC Kit; Vector Laboratories Inc., Burlingame, CA). Diaminobenzidine will be used as chromogen. 57B staining will be classified as follows: no staining; “weak,” indicating low-intensity staining regardless of positive cell percentages or medium intensity staining of no more than 20% of cells; “moderate,” indicating medium-intensity staining of more than 20% of cells or high-intensity staining of no more than 20% of cells; “strong,” indicating high-intensity staining of more than 20% of cells. Only

moderately and strongly positive cases will be considered positive. For PCR based analysis, total RNA will be isolated from collected tissue samples and reverse transcribed to cDNA using standard methods. The expression of tumor antigens from cDNA samples will then be interrogated using real-time PCR and a variety of specific tumor antigen probes.

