#### **12.5.2.8 Immune Response**

Section 10.2.1 details how samples are run in duplicate or triplicate using ICS via flow cytometry or ELISPOT. The first step in the analysis of immunologic response will be to form the subject average across the duplicate or triplicate measurements recorded at each time point. In situations where only one measurement is obtained, the single value will be used in the analysis. If any values are in the range (0,1) inclusive, a value of 0.5 will be used in the analysis of count information on the log10 scale.

The observed and log10 transformed values will be summarized for each visit. In addition, the change from baseline will also be summarized descriptively. At each visit and for the last available visit, a sign-rank test will be used to evaluate the null hypothesis that the change from baseline is centered at zero separately for each of the dosing groups. Similarly, a Wilcoxon rank-sum test will be used to evaluate the null hypothesis that the observed and change from baseline values have a similar location ((i.e. median) between the low and high dose groups.) A 95% CI for the ratio of the differences geometric mean will be obtained by back-transforming the 95% non-parametric CI for the difference in log10 analysis. For the purposes of identifying the most important comparison, the analysis of the last assessment will be considered the primary analysis with other time points considered secondary analyses. Additionally, a repeated measures analysis will be completed modeling log10 transformed values as a function of visit, treatment, and a visit

by treatment interaction. Model results may not be reported if convergence is unattainable because of the small sample size.

These analyses will be completed using the ITT and Per-Protocol populations.

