- Proportion of patients with progressive disease at 3, 6, 12, 18, and 24 months from randomization. Progressive disease is defined as an increase in T stage from TIS or Ta (at screening) to T1 (lamina propria invasion), development of T2 or greater or lymph node (N+) disease or distant metastasis (M1), or an increase in grade from low to high per the IBCG recommendations.
- Disease-Free survival at 3, 6, 18, and 24 months from randomization. A patient is considered as disease-free at a timepoint if the disease has not recurred nor progressed, and the patient is still alive.
- Overall Disease free survival (DFS): DFS is the time from randomization until the day of disease recurrence or progression
- Overall survival (OS): OS is the time from randomization until the day of death by any cause or censoring
- Proportion of patients undergoing a repeat TURBT by 12 months and by 24 months from randomization
- Proportion of patients undergoing cystectomy by 12 months and by 24 months from randomization
- Immunological response (IR): Peripheral blood immunological response via intracellular cytokine staining (ICS) by ELISPOT of on CD8+ cells following HS-410 vaccination will also be evaluated

Phase 2 only:

- Safety of the combination of vesigenurtacel-L and BCG
- Safety of high dose vesigenurtacel-L monotherapy

Exploratory Endpoints

In patients completing at least 6 weekly doses of study medication, the following exploratory endpoints will be evaluated:

- Immunologic response of PBMCs (analysis of surface markers, CD3, CD4, CD8, degranulation) and stimulation analysis via ICS of IFN- γ , IL-2, TNF α and perforin.
- Total PBMC counts by flow cytometry, including lymphocyte subsets (B cells, helper T-cells, cytotoxic T-cells, NK cells and T-reg)

- Evaluation of tumour tissue obtained from pre-treatment resection for antigen expression by immunohistochemical analysis
- Evaluation of tumour tissue obtained from repeat biopsy, if clinically indicated, for presence of infiltrating T-lymphocytes
- T cell receptor sequencing of peripheral blood T cells before and during the course of treatment
- Immune cell infiltration and inflammatory cytokine levels in urine (phase 2 only)

Safety Endpoints

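### SAP 5.3 lists two post-randomisation variables, immune response and TIL status, as efficacy subgroups, and TIL status is known only for patients who had a clinically indicated biopsy

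*SAP*

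**What the plan says.** For Phase 2, SAP 5.3 states that "the following subgroups may be used to further summarize and evaluate the efficacy endpoints, if sufficient data are available". The list that follows mixes baseline characteristics (risk group, CIS, stage and grade, prior BCG, tumour number and size) with "Patient immune response" and TIL status. It gives no specimen, timepoint, cut-off or landmark for these two, and no rule for patients without a value. SAP 5.1 rules out imputation.

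Immune response is defined in Protocol 10.2.1: "Positive responses will be defined as a greater than two-fold increase in the number of" IFNγ-positive CD8+ T cells compared with baseline. Phase 2 samples are scheduled at baseline and Weeks 7, 13, 28 and 56 (Protocol 6.2.1). For the immunologic analysis itself, Protocol 12.5.2.8 says "the analysis of the last assessment will be considered the primary analysis with other time points considered secondary analyses".

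For TILs, the exploratory endpoint in SAP 2.1 is "Evaluation of tumour tissue obtained from repeat biopsy, if clinically indicated, for presence of infiltrating T-lymphocytes". Protocol 3.4.3 and 10.2.5 likewise place the assay on repeat or post-treatment biopsies. Pre-treatment tissue is collected for "screening the tissue for representative antigen expression", MHC class I and immunosuppressive molecules (Protocol 10.2.6), and no TIL assay is named there. A negative biopsy, where one is indicated, is also part of the definition of disease-free status (Protocol 10.1).

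Protocol 12.5.2.9 separately plans to compare immune responders with non-responders across all four arms on recurrence, progression, DFS, TURBT or cystectomy, and survival. It sets no landmark.

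**The concern.** A subgroup treatment effect keeps the protection of randomisation only if the subgroup is defined by something fixed before treatment. Neither of these variables is.

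Immune response is what the vaccine is designed to cause. A placebo responder crossed the threshold without vaccine, whereas a vaccine responder may have crossed it because of vaccine. Comparing arms within responders therefore compares different kinds of patients.

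TIL status has an additional problem, because whether the variable exists at all depends on a biopsy having been indicated. A patient with clean cystoscopies and cytology would normally have no value. The subgroup is thus selected through a step close to the endpoint, and arms with different failure rates will be selected to different degrees.

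The risk is that efficacy estimates with 95% confidence intervals by responder or TIL group are read as a biomarker signal and carried into the design of the next trial.

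**Working it through.** **Plan's own figure.** With 23 evaluable patients per arm (SAP 4), 60% against 90% disease-free (Protocol 12.6.2) and one-sided alpha 0.10, exact enumeration of Fisher's test gives power 0.808. The stated 80% reproduces. This confirms 60% and 90% as the working rates, and nothing below depends on the power.

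**TIL status: inputs.**
- n = 25 per arm (Protocol 3.3).
- Disease-free proportion at one year, p: 0.60 control and 0.90 in each vaccine arm (Protocol 12.6.2).
- s = probability of biopsy among patients who fail by one year, and f = probability of biopsy among disease-free patients. The documents give neither, so both are assumptions, taken as equal across arms.

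**Expected failures.** 25 × (1 − 0.60) = 10.0 in control; 25 × (1 − 0.90) = 2.5 in each vaccine arm.

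**Formulas.**
- Patients with a TIL value: N = 25 × [(1 − p)s + pf].
- Disease-free share among them: pf / [(1 − p)s + pf].

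Example with s = 1 and f = 0.10:
- Control: N = 25 × (0.40 + 0.06) = 11.5; share = 0.06 / 0.46 = 13%.
- Vaccine: N = 25 × (0.10 + 0.09) = 4.75; share = 0.09 / 0.19 = 47%.

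| s | f | N control | N vaccine arm | Disease-free, control | Disease-free, vaccine | Difference (points) |
|---|---|---|---|---|---|---|
| 1.0 | 0 | 10.0 | 2.5 | 0% | 0% | 0 |
| 1.0 | 0.10 | 11.5 | 4.75 | 13% | 47% | 34 |
| 1.0 | 0.20 | 13.0 | 7.0 | 23% | 64% | 41 |
| 1.0 | 0.30 | 14.5 | 9.25 | 31% | 73% | 42 |
| 0.8 | 0.10 | 9.5 | 4.25 | 16% | 53% | 37 |
| 0.8 | 0.20 | 11.0 | 6.5 | 27% | 69% | 42 |

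The assumed truth is the same in every row: 60% against 90%, a 30-point difference. The difference among patients with a TIL value runs from 0 to 42 points according to biopsy practice alone, before any split into TIL-high and TIL-low. With s = 1, the fraction of the arm with a value is 10.0/25 = 40% to 14.5/25 = 58% in control, against 2.5/25 = 10% to 9.25/25 = 37% in a vaccine arm. Availability therefore differs by arm even with identical biopsy rules.

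**Immune response: timing.** Week 56 is Day 386 (Protocol 6.2.1). The primary endpoint is targeted at Day 366 (SAP 7.1), so the last scheduled sample falls 386 − 366 = 20 days after it. Patients who stop dosing early have an end-of-treatment sample about four weeks after their last dose (Protocol 6.2.3.14). They contribute fewer samples, and the last of these may follow the recurrence. Without a landmark, classification can come after the outcome, and patients who stay on schedule have more chances to be called responders. The documents give no response rates, so no size is put on this.

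**The case against.** The strongest reply is that the harm is already limited. These subgroups are optional and depend on sufficient data. SAP 5.5 confines p-values to the primary analysis and describes the trial as hypothesis-generating. SAP 7.3 sends immunologic summaries to a separate plan, where a landmark could be set. All of that is true and keeps the severity low. It does not cure the list: a data-sufficiency condition addresses numbers and not selection, and a biased estimate with a confidence interval misleads without a p-value.

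Second, TIL status is undefined in SAP 5.3. Pre-treatment tissue is collected and SAP 7.3 mentions tissue immune-cell infiltration, so a baseline assay is not excluded. This stands: if that is what is meant, the item can stay once the SAP says so.

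Third, several stronger readings are tempting but not supported:
- A reader might infer that patients with a TIL value are almost all failures. That holds only if no disease-free patient is biopsied. Biopsies can be negative, and a patient with CIS at screening may have evidence of CIS at 3 months and be disease-free by 6 months (Protocol 10.1, 12.5.2.4).
- A reader might infer that the subgroup conditions on recurrence itself. It conditions on suspected disease, which is closely tied to the endpoint but not identical.
- The explicit trigger, "biopsy if area suspicious for disease recurrence is identified at discretion of investigator", is in Protocol 6.3 and governs long-term follow-up. For patients who complete treatment, that begins after Day 386. The first-year visits say only that biopsy is done if indicated, per standard of care. Suspicion as the trigger at those visits is a reasonable inference, not a stated rule.
- A reader might want a hazard ratio for the immune-response bias. It would need response and discontinuation rates that the documents do not give. It would also describe responders against non-responders, which is a different comparison from arms within responders.

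**Conclusion.** The concern holds, at low severity. Two of the subgroup factors in SAP 5.3 are post-randomisation variables, and efficacy estimates within them cannot be read as treatment effects. For immune response this follows from its definition as a change after baseline. For TIL status it follows from the only assay described, on clinically indicated biopsies, and it would fall away if a pre-treatment assay were intended.

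The illustrated size for TIL status is a disease-free rate of 0% to 31% (control) and 0% to 73% (vaccine) among patients with a value, against 60% and 90% overall. It assumes that all failures and 0% to 30% of disease-free patients are biopsied, equally across arms. It shows that the result depends on biopsy practice and does not predict what the trial would find. The primary ITT analysis does not use either variable and is unaffected.

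**What to change.** 1. Limit the SAP 5.3 subgroups to baseline factors by removing immune response and TIL status. Keep TIL status only if a pre-treatment assay is meant, and then state the specimen, timepoint and cut-off.
2. Report TIL findings descriptively among biopsied patients, by arm, with the number biopsied in each arm.
3. Analyse immune response against efficacy only by a landmark (for example Week 7 or Week 13) or a time-dependent method, stratified by arm and labelled a non-randomised association. Apply the same rule to the responder comparison in Protocol 12.5.2.9. Otherwise the timing problem remains there after the SAP list is corrected.
4. State that a landmark removes the timing bias but does not make responders comparable between arms.

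The cost is two deleted lines and a few added sentences. Two optional exploratory tables are lost or changed. Sample size, data collection and the primary analysis stay as they are.

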5.4 Interim Analyses and Data Monitoring

This is a phase 1/2 exploratory trial. Therefore, a formal interim analysis will not be conducted. A Data Monitoring Committee (DMC) will convene after all 10 patients are enrolled in Phase 1 to confirm the study will proceed to Phase 2.

The data collection instrument for this study is a Heat Biologics-defined CRF. Patient data necessary for analysis and reporting will be entered/transmitted into a validated database or data system. Sponsor's clinical data associates (or designees) will review all source-verified CRFs for logical consistency and will use automated programs to help identify missing data, selected protocol violations, out-of-range data, and other inconsistencies. Data clarification or correction will continue until appropriate resolution. Listings of patient data by dataset and/or by patient will be monitored by the DMC as per the DMC charter.

5.5 Multiple Testing

The proposed phase 1/2 trial is exploratory, focused on learning and hypothesis generation. Therefore, the preservation of the overall significance level is of lesser importance. However, to address the hazards associated with multiple statistical testing, p-values will only be generated for the primary analysis comparing the two doses of the experimental vaccine to the placebo control. The secondary and exploratory endpoints will be presented as point estimates with associated 95%CI.

6 Summary of Study Data

6.1 Subject Disposition

For each of the analysis populations, the number and percentage of patients by treatment group will be provided. In addition, the number of patients in the ITT Population will be summarized by study site and treatment group. The number and percentage of patients discontinuing treatment will be summarized according to reasons of discontinuation as documented in the CRF (e.g. dosing noncompliance, AE, prohibited medications, consent withdrawal). In addition, the number and percentage of patients entering long-term follow-up and completing/discontinuing the follow-up will be presented.

6.2 Protocol Deviations

Major protocol deviations could impact the analysis. Protocol deviations specified in Protocol Section 13.3 will be captured in the CRF and reviewed by a medical monitor for determination of impact on patient inclusion in the Per Protocol population:

- Entered into the study without meeting eligibility criteria
- Developed withdrawal criteria during the study and was not withdrawn
- Received wrong treatment or incorrect dose
- Received excluded concomitant treatment
- Failed to collect data necessary to interpret primary endpoints

Protocol deviations will be listed by treatment group, patient number, and categorized according to the deviation reasons. If a significant number of deviations occur, a summary table will be produced showing the number of patients for each deviation reason. Study withdrawal by reasons collected in

the CRF (e.g., eligibility criteria violation, prohibited concomitant treatment, etc.) will also be summarized.

6.3 Demographic and Baseline Variables

For both the phase 1 and 2 parts of the study, the following patient baseline demographics and disease status variables will be summarized by treatment group for the ITT Population:

Demography: Age, sex, race and ethnicity

Stratification factors: Risk of recurrence (High risk vs intermediate risk), carcinoma in situ (yes vs no)

Bladder cancer history: histopathologic type, TNM stage, carcinoma in situ, severity, newly diagnosed disease vs recurrent disease, time from last BCG treatment to screening (for patients with recurrent disease)

Phase 1 Risk assessment: Number of tumors, tumor diameter, prior recurrence rate, category (Ta / T1), concurrent CIS, Grade (WHO 1973), total recurrence score, total progression score

Baseline vital signs: Weight, height, systolic blood pressure, diastolic blood pressure, heart rate, body temperature and respiratory rate

Selected baseline laboratory, including lab values dictating inclusion/exclusion:

- Hematology: White blood cell (WBC) count, neutrophils, platelets, hemoglobin, lymphocytes, red blood cell (RBC) count
- Chemistry: ALT, AST, Alkaline phosphatase, Albumin, total bilirubin, serum creatinine, creatinine clearance

No statistical tests to check homogeneity between treatment groups at baseline will be performed.

6.4 Medical History

Medical history will be coded using MedDRA dictionary version 18 or higher, and will be summarised by MedDRA preferred term and system organ class.

6.5 Prior and Concomitant Medications

Prior and concomitant medications will be coded using World Health Organization (WHO) drug dictionary version March 2013 (or higher), and will be summarised by preferred term and/or ATC class. Medications administered prior to the expected first dose of study will be considered prior medications. Concomitant therapies will be those that are taken on or after Study Day 1 through 30 days after the last dose of study drug. Medications started prior to Study Day 1 and continued into the treatment period will be included in the summary of concomitant therapies. Incidence of prior medication and concomitant therapies will be summarized by preferred term.

7 Efficacy Analyses

All efficacy analyses for recurrence or progression will use standard TNM disease staging, specifically with the following T stage hierarchy: Ta<TIS<T1<T2<T3<T4, and Low Grade<High Grade.

